7.4 Final Study Visit 08 – Day 10 (+/- 2 days)

- Vital signs including oral temperature, blood pressure, and pulse will be obtained.
- A targeted physical exam may be performed, if indicated.
- Review concomitant medications
- Review for AEs and SAEs.
- Collect 10 mL of blood for oxfendazole level.
- Collect 15 mL of blood for safety panels (hemoglobin, white blood cell count, including neutrophil count, platelet count, INR, partial thromboplastin time, Na, K, Cl, CO₂, blood urea nitrogen, creatinine, ALT, AST, and total bilirubin).
- Collect urine for dipstick testing for protein and glucose.
- Counseling on avoidance of pregnancy.

7.5 Enrollment/Baseline- GROUP 4

Clinic Visit 01, Day 1

Eligible subjects will be asked to return to the Clinical Research Unit (CRU) having fasted for 8 or more hours.

General

- Review inclusion/exclusion criteria (including assessment of time of last oral food intake and laboratory results obtained at the screening visit, Day 00).
- Randomize to either fasting (water is permitted) or fed using the IDES system
- Review concomitant medications including confirmation of absence of medications in the past 48 hours.
- A brief interim medical history will be taken.
- A routine physical examination that assesses general appearance and the following areas/systems, including skin, lymph nodes, HEENT, neck, respiratory, cardiovascular, pulmonary, abdomen, extremities, musculoskeletal, and neurological will be performed by a clinician licensed to make diagnoses.
- Vital signs including oral temperature, blood pressure, and pulse will be obtained.
- Perform a urine pregnancy test for females of childbearing potential.
- A heparin lock will be inserted, blood will be drawn (10 mL) for baseline PK (prior to product administration), and (15 mL) for safety labs (hemoglobin, white blood cell count, including neutrophil count, platelet count, INR, partial thromboplastin time, creatinine, Na, K, CL, CO₂, blood urea nitrogen, ALT, AST, and total bilirubin).
- Collect urine for dipstick testing for protein and glucose.
- For subjects randomized to receive a high fat meal during the first dose, provide high fat breakfast. For subjects randomized to receive the first dose following an 8 hour fast, proceed to next steps without providing food.

Administration of Study Medication

A study nurse will administer a single 3 mg/kg oral dose of oxfendazole to the subject.

- Fasting (water is permitted) subjects will remain fasting (water is permitted) for two hours after the administration of drug.
- Fed subjects will receive a high fat breakfast. Approximately 30 minutes (+/- 15 minutes) following completion of the meal, the study nurse will administer a single 3 mg/kg oral dose of oxfendazole.
- Lunch and dinner will be provided. Subjects will be allowed to eat snacks but will be asked to avoid drinking grapefruit juice and excessive (>2 cups) coffee.
- 10 mL of blood for oxfendazole level will be drawn at 30 minutes, 1, 2, 3, 4, 6, 9, and 12 hours (all times have a window of +/- 15 minutes except the 9 and 12 hour samples which have a window of +/- 30 minutes- it is critical to record the exact time of blood draw).
- Perform EKG approximately 2 hours following study drug (+/- 20 minutes)
- Assess AEs and SAEs throughout the day and prior to discharge from the CRU.
- Counsel on need to avoid alcohol, drugs, tobacco and medications throughout the study.
- Counseling on avoidance of pregnancy.

7.6 Follow-up – GROUP 4

Clinic Visit 02, Day 2

- Vital signs including oral temperature, blood pressure, and pulse will be obtained.
- A targeted physical exam may be performed, if indicated.
- Review concomitant medications
- Review for AEs and SAEs
- Draw 10 mL of blood for oxfendazole level -approximately 24 hours after dosing on day 1 (+/- 4 hours)
- Counsel on need to avoid alcohol, drugs, tobacco and medications throughout the study.

Clinic Visit 03, Day 4

- Vital signs including oral temperature, blood pressure, and pulse will be obtained.
- A targeted physical exam may be performed, if indicated.
- Review concomitant medications
- Review for AEs and SAEs
- Collect 15 mL of blood for safety panels (hemoglobin, white blood cell count, including neutrophil and eosinophil counts, platelet count, INR, partial thromboplastin time, Na, K, Cl, CO₂, blood urea nitrogen, creatinine, ALT, AST, and total bilirubin).
- Collect urine for dipstick testing for protein and glucose.
- Remind subjects to remain fasting (water is permitted) for 8 or more hours prior to study visit 04.

-
- Counsel on need to avoid alcohol, drugs, tobacco and medications throughout the study.

Clinic Visit 04, Day 8 (+/- 1 day)

- Vital signs including oral temperature, blood pressure, and pulse will be obtained.
- Review inclusion/exclusion criteria (including assessment of time of last oral food intake).
- Perform a urine pregnancy test for females of childbearing potential.
- A targeted physical exam may be performed, if indicated.
- Review concomitant medications
- Review for AEs and SAEs
- A heparin lock will be inserted, blood will be drawn (10 mL) for baseline PK (prior to product administration)

Administration of Study Medication

A study nurse will administer a single 3 mg/kg oral dose of oxfendazole to the subject.

- For subjects who fasted during the first day of study drug administration, provide high fat breakfast prior to study drug administration. Approximately 30 minutes (+/- 15 minutes) following completion of the meal, the study nurse will administer a single 3 mg/kg oral dose of oxfendazole.
- For subjects who received a meal prior to the first day of study drug administration, subjects should fast for 8 hours prior to receipt of study drug and remain fasting (water is permitted) for two hours after the administration of drug.
- Lunch and dinner will be provided. Subjects will be allowed to eat snacks but will be asked to avoid drinking grapefruit juice and excessive (>2 cups) coffee.
- 10 mL of blood for oxfendazole level will be drawn at 30 minutes, 1, 2, 3, 4, 6, 9, and 12 hours (all times have a window of +/- 15 minutes except the 9 and 12 hour samples which have a window of +/- 30 minutes- it is critical to record the exact time of blood draw).
- Perform EKG approximately 2 hours following study drug (+/- 20 minutes)
- Assess AEs and SAEs throughout the day and prior to discharge from the CRU.
- Counsel on need to avoid alcohol, drugs, tobacco and medications throughout the study.
- Counseling on avoidance of pregnancy.

Clinic Visit 05, Day 9: (or 1 day following second dose)

- Vital signs including oral temperature, blood pressure, and pulse will be obtained.
- A targeted physical exam may be performed, if indicated.
- Review concomitant medications
- Review for AEs and SAEs

-
- Draw 10 mL of blood for oxfendazole level -approximately 24 hours after dosing on day 8 (+/- 2 hours)
 - Counsel on need to avoid alcohol, drugs, tobacco and medications throughout the study.

7.7 Final Study Visit 06 Day 14 (+/- 2 days) - GROUP 4

- Vital signs including oral temperature, blood pressure, and pulse will be obtained.
- A targeted physical exam may be performed, if indicated.
- Review concomitant medications
- Review for AEs and SAEs
- Draw 10 mL of blood for oxfendazole level
- Collect 15 mL of blood for safety panels (hemoglobin, white blood cell count, including neutrophil count, platelet count, INR, partial thromboplastin time, Na, K, Cl, CO₂, blood urea nitrogen, creatinine, ALT, AST, and total bilirubin).
- Collect urine for dipstick testing for protein and glucose.
- Counseling on avoidance of pregnancy.

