Description of Study Design:	This Phase I study is an open label evaluation of the safety and pharmacokinetics of escalating oral doses of oxfendazole (3 mg/kg, 7.5 mg/kg or 15 mg/kg) given daily for five days in healthy volunteers. Up to eight volunteers will be enrolled and receive one oral dose of 3 mg/kg given daily for 5 days. To enhance safety, one sentinel subject will be enrolled and followed for 7 days for defined safety events. A second sentinel subject will then be enrolled and followed for 7 days. If no

[figure not shown]
predefined safety events are identified, the remaining six subjects in this group will be enrolled. All volunteers will be followed for 10 days and pharmacokinetic, safety laboratory and EKG studies will be performed as outlined in the study visit table in Appendix A. A safety review of the electronic data will be completed and the DMID Medical Monitor will receive a dose escalation report from the Statistical and Data Coordinating Center (SDCC) including whether dose escalation halt criteria were or were not met. If no predefined safety events occur after all eight subjects have completed the day 10 visit, the DMID Medical Monitor will issue approval to proceed with enrollment of the second group of eight subjects will be enrolled to receive five days of 7.5 mg/kg of oxfendazole using the same enrollment plan as outlined above. If no predefined safety events are encountered, the third group of eight subjects will be enrolled to receive five days of 15 mg/kg using the same enrollment plan. A fourth group of 12 subjects will participate in a single dose cross over evaluation of the effects of food on the pharmacokinetics of oxfendazole. Half of these subjects will fast for 8 hours and then will receive a single dose of 3 mg/kg of oxfendazole on day 1. The other half will receive a single dose of 3 mg/kg of oxfendazole following a high fat breakfast. All 12 subjects will be followed for seven days and on day 8 each subject will cross over to receive drug following a high fat breakfast or following an 8 hour fast and will be followed for another seven days. Pharmacokinetic studies will be performed for 24 hours following each dose of oxfendazole.

Group	N	Study Dose	Timing of Study Dosing
1	8	3 mg/kg	Days 1-5
2	8	7.5 mg/kg	Days 1-5
3	8	15 mg/kg	Days 1-5

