3.2 Study Outcome Measures

3.2.1 Primary endpoint:

- The rate of adverse events (AEs) related to oxfendazole within 10 days of receipt of oxfendazole given for 5 sequential, daily oral doses of either 3, 7.5 or 15 mg/kg
- The rate of adverse events (AEs) related to oxfendazole within 7 days of receipt of oxfendazole given as a single daily dose of 3 mg/kg on days 1 and 8 either following an 8 hour fast or following a high fat meal.

3.2.2 Secondary endpoints:

- Plasma C_{max}, T_{max}, AUC, T_{1/2} of oxfendazole at specified time points following each dose of a 5 day daily regimen of either 3, 7.5 or 15 mg/kg
- Plasma C_{max}, T_{max}, AUC, T_{1/2} of oxfendazole at specified time points following a single dose of oxfendazole of 3 mg/kg on days 1 and 8 administered after an 8 hour fast or after a high fat meal.

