4 STUDY DESIGN

This Phase I study is an open label multiple ascending dose evaluation of the safety and PK of oxfendazole (3, 7.5, or 15 mg/kg) in healthy adult men and nonpregnant women aged 18-45 (inclusive) followed by a single dose cross over trial evaluating the safety and pharmacokinetics of a single dose of oxfendazole (3 mg/kg) given following an 8 hour fast or following a high fat meal. In the multiple ascending dose evaluation, each dose group will be comprised of eight volunteers. In the food effects evaluation, evaluating the effects of food on drug absorption, 12 subjects will be enrolled into the single dose cross over group where half of the subjects will initially receive a single dose of 3 mg/kg of oxfendazole following an 8 hour fast and the other half will receive a single dose of 3 mg/kg of oxfendazole following a high fat meal. Subjects will then cross over to receive a single dose following a high fat breakfast or fasting period (water is permitted). All subjects will have received a single dose of oxfendazole (3 mg/kg) following both a fasting period and a meal.

For the multiple ascending dose evaluation, each subject in the first dose group (3 mg/kg) will receive an oral daily dose of oxfendazole for five sequential days and will be monitored for a total of 10 days. Each subject will be followed with blood, urine and EKG studies for safety and will provide plasma samples for oxfendazole PK studies as outlined in the study visit schedule in Appendix A. To enhance safety, one sentinel subject will be dosed for five days and monitored for 7 days from the time of the first dose for predefined adverse events, which will include any drug related SAEs, any study drug-related Grade 3 AEs or laboratory abnormalities or two study drug-related Grade 2 AEs or laboratory abnormalities in the same laboratory parameter. If there are no predefined safety events, a second sentinel subject will be enrolled and followed for a total of 7 days. If there are no predefined safety signals identified for either of these two sentinel subjects, the remaining subjects in the group will be enrolled.

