After all eight subjects have completed the 10 day follow up period, an electronic safety review of the electronic data will be performed and the SDCC will issue a report to DMID stating that the predefined halting rules have or have not been met. If none of the predefined safety events (any study drug related SAE, any study drug related Grade 3 AE or laboratory abnormality or two study drug related Grade 2 AEs or laboratory abnormalities in the same laboratory parameter) have occurred (one study drug related two sequential subjects (one at a time with 7 days between each subject) DMID will approve enrollment into the second dose group (7.5 mg/kg oxfendazole daily x 5 days) and will be monitored for a total of 7 days each for predefined adverse events prior to enrolling the remaining subjects in the group. After the 10 day follow up period has been completed for group 2, an electronic safety review will be completed and if no predefined events have occurred two sequential subjects (one at a time with 7 days between each subject) will be enrolled into the third dose group (15 mg/kg oxfendazole daily x 5 days) and will be monitored for a total of 7 days each for predefined safety events prior to enrolling the remaining subjects in the group.

For the multiple ascending dose evaluation, between 8 and 24 subjects will be enrolled. This number should be small enough to perform the study safely and efficiently, yet large enough for an estimation of the oxfendazole PK and the identification of any common side effects of oxfendazole following multiple doses.

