Subjects will be administered oxfendazole by a study nurse or investigator on days 1, 2, 3, 4 and 5. Subjects will be fasting (water is permitted) for eight hours prior to, and for two hours after, the administration of drug. On the 1st and 5th day of drug administration intensive blood sampling will be performed for PK studies (pre-dose and 30 minutes, 1, 2, 3, 4, 6, 9, and 12 hours following the dose). On days 2, 3 and 4, blood sampling for PK studies will be performed prior to each dose and 2 hours after each dose. On day 6, blood sampling for PK studies will be performed approximately 24 hours following the dose on day 5. Monitoring will start immediately after dosing and will continue for 10 days. Safety laboratories will be performed on days 1, 3, 5, 8 and 10. EKG studies will be performed at screening, two hours after doses on days 1, 3 and 5, and day 8. Subjects will be interviewed to monitor for AEs and SAEs. Blood sampling for PK studies will be performed on days 8 and 10. In addition, prior to study drug administration on days 2-5, if subjects self-report any new signs or symptoms a targeted physical exam may be performed, if indicated, and the new signs or symptoms will be recorded as an AE or SAE as appropriate.

Following blood sampling performed on each day of dosing, subjects will be allowed to return home. Subjects will be counseled to avoid drug, alcohol and tobacco use through the end of the study (Day 10 for groups 1-3 and Day 14 for group 4).

In the food effects evaluation, 12 subjects will be enrolled into the single dose cross over group. Group 4 can be enrolled concurrently with groups 1, 2, and 3. In group 4, half of the subjects will receive a single dose of 3 mg/kg of oxfendazole following an 8 hour fast and the other half will receive a single dose following a high fat meal. Each subject will be followed with safety laboratories, EKGs and PK studies for 7 days at which time they will cross over to receive a single dose of oxfendazole (3mg/kg) following either a high fat meal or following an 8 hour fast.

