9.3 Reporting Procedures

AEs will be documented from the time of receipt of study drug on Day 1 (Visit 02) through the final study visit (approximately 10 or 14 days after receipt of study product).

SAEs will be documented from the time of receipt of study drug on Day 1 (Visit 02) through the final study visit.

AEs will be followed until resolution even if this extends beyond the study-reporting period. Resolution of an AE is defined as the return to pretreatment status or stabilization of the condition with the expectation that it will remain chronic.

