9.5.2 Dose Escalation Halting Criteria

Prior to dose escalation to the next cohort, the Statistical and Data Coordinating Center (SDCC) will notify the study PIs, DMID medical monitor (MM), and DMID Independent Safety Monitor (ISM) whether the below dose escalation criterion were met. Following enrollment and 10 days of safety follow up of the eight subjects in the dose group.

Dose escalation will not proceed if any of the following dose escalation criteria occur:

- any study drug related SAE
- any study drug related grade 3 AE or laboratory abnormality
- any two Grade 2 AE or laboratory abnormalities of the same laboratory parameter

In addition to these criteria, dose escalation may also stop for other reasons per the advice of the SMC, ISM, or DMID Medical Monitor for further evaluation, discussion, and recommendations from the SMC.

If the above dose escalation halting criteria are NOT met, the dose escalation may proceed with agreement of DMID.

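### In Groups 1-3 the two-sided window on the Day 10 visit lets the last scheduled adverse event review and safety panel fall before the 10 days that the endpoint and dose escalation call for (minor, cheap to fix).

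*Protocol*

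**What the plan says.** Three parts of the protocol bear on how long subjects in Groups 1-3 are followed.

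- **The period wanted.** Section 3.2.1 defines the primary endpoint as "The rate of adverse events (AEs) related to oxfendazole within 10 days of receipt of oxfendazole given for 5 sequential, daily oral doses". Section 4 says that each subject "will receive an oral daily dose of oxfendazole for five sequential days and will be monitored for a total of 10 days". It places the electronic safety review "After all eight subjects have completed the 10 day follow up period", and Section 9.5.2 places the escalation decision "Following enrollment and 10 days of safety follow up of the eight subjects in the dose group".
- **The visit that closes the period.** Section 7.4 gives "Final Study Visit 08 – Day 10 (+/- 2 days", and Appendix A repeats the window. The visit includes an AE review and the full safety panel. Nothing is scheduled after it in these groups. Section 9.3 documents AEs "through the final study visit (approximately 10 or 14 days after receipt of study product".
- **The escalation trigger in the Protocol Summary.** Here the condition is worded by visit rather than by days: "If no predefined safety events occur after all eight subjects have completed the day 10 visit".

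Section 3.2.1 does not say which dose starts the 10 days. Section 4 describes subjects avoiding drugs, alcohol and tobacco "through the end of the study (Day 10 for groups 1-3 and Day 14 for group 4". That points to study Days 1-10 counted from the first dose, and I use that count.

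**The concern.** The sponsor chose 10 days both for the primary safety endpoint and for the follow-up before the next dose level, but the visit window does not guarantee 10 days. A subject seen early and within the window is complete by visit and incomplete by days. No scheduled procedure then covers the remainder.

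The gap is specific. After an early last visit, a new non-serious event on Day 9 or 10 is found only if the subject reports it. A laboratory change without symptoms has no scheduled test. Section 2.3.1 names bone marrow and liver as the main target organs in animals, so laboratory findings matter in this study. Under Section 9.5.2 one drug-related Grade 3 laboratory abnormality, or two Grade 2 abnormalities in the same parameter, stops escalation.

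The two forms of the escalation trigger also diverge in this case. An early in-window visit could meet the Summary wording. Sections 4 and 9.5.2 separately ask for 10 days. No step says how the two are reconciled.

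**Working it through.** **Inputs.** Visit 08: Day 10, window 2 days either way (Section 7.4, Appendix A). Visit 07: Day 8, window 1 day either way, with its own AE review and safety panel (Section 7.3). Doses on Days 1-5 (Section 6.2.1). Period: 10 days (Sections 3.2.1, 4 and 9.5.2). Single-dose half-life: 8.5-11 hours (Section 2.1.2).

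**Step 1: the plan's own figure.** With the first dose on Day 1, a visit on Day 10 closes 10 study days. The nominal schedule matches the stated period.

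**Step 2: the permitted range.** 10 - 2 = Day 8 and 10 + 2 = Day 12.

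**Step 3: shortfall for each permitted day.** Shortfall = 10 - visit day, with a floor of 0. Days from the last dose to the last panel = visit day - 5.

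| Visit 08 on | Study days short of Day 10 | Days after dose 5 |
|---|---|---|
| Day 8 | 2 | 3 |
| Day 9 | 1 | 4 |
| Day 10 | 0 | 5 |
| Day 11 | 0 | 6 |
| Day 12 | 0 | 7 |

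**Step 4: which early day is realistic.** Visit 07 may fall on Days 7-9. For Visit 08 to fall on Day 8, Visit 07 must be on Day 7 or share Day 8. If Visit 07 is on its nominal day and the visits are on separate days, the earliest Visit 08 is Day 9. The likelier shortfall is therefore 1 day. No minimum spacing between the two visits is stated, so 2 days remains possible.

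**Step 5: sensitivity to the starting point.**

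- Ten elapsed days from the first dose (to Day 11): for visits on Days 8 to 12 the shortfall is 3, 2, 1, 0, 0.
- Ten elapsed days from dose 5 (to Day 15): 7, 6, 5, 4, 3.

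Under either count even the nominal Day 10 visit would be short, by 1 or 5 days. That is a further reason to read the plan as study Days 1-10, which is also the count that gives the smallest gap.

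**Step 6: drug left at an early visit.** Fraction of dose 5 remaining = 2^(-hours / half-life), assuming that the single-dose half-life holds on repeat dosing.

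- Day 8 (72 hours): 2^(-72/8.5) = 0.28% to 2^(-72/11) = 1.07%.
- Day 9 (96 hours): 2^(-96/8.5) = 0.04% to 2^(-96/11) = 0.24%.

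**Step 7: the window after the fix.** With Day 10 (+2 days) the permitted days are 10, 11 and 12, and the shortfall is 0 on each.

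**The case against.** The best defence is that the 10 days are nominal. Section 9.3 qualifies the period as approximate, the Summary speaks of a visit, and a symmetric window is ordinary practice. On that view an exact 10 days for every subject is a preference. This carries weight for the AE tabulation, which is descriptive: Section 11.1 plans estimation without hypothesis testing. It carries less for escalation, where Sections 4 and 9.5.2 state 10 days without qualification.

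Other safeguards narrow the gap, and they stand:

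- Abnormalities already present at an early visit are followed until resolved or stable (Section 9.2.3).
- Laboratory tests may be repeated if an AE calls for it (Section 8.2.1), and unscheduled visits may take place after the final visit (Section 7.9).
- Related serious events learned of later are still reported (Section 9.3.1).
- Escalation needs DMID agreement, and the SMC, the ISM or the medical monitor may advise stopping for other reasons (Section 9.5.2).
- The second sentinel is dosed at least 7 days before the remaining six. When one of those six reaches Day 8, that sentinel is at study Day 15 or later (8 + 7). This supplies calendar time for both sentinels, though no extra scheduled test if their own last visits were early.

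A reader might infer that escalation can properly go ahead on fewer than 10 days of data. The documents do not support this. Sections 4 and 9.5.2 can be applied together with the Summary, the stricter condition governing, and an early visit alone would not meet them. What remains is an unreconciled wording, not a permission.

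A reader might also infer that events on Days 9-10 cannot be recorded once the last visit has passed. That goes too far as well. Section 5.2 refers to a 10-day study period, and Section 7.9 allows later visits for events within it. Such events can be recorded but are not actively sought.

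**Conclusion.** The mismatch is real and small. The window permits the last scheduled AE review and safety panel on Day 9, 1 study day short, or less plausibly on Day 8, 2 days short. It affects only new non-serious or symptomless events that first arise on Day 9 or 10. By then about 1% or less of the last dose remains, if the single-dose half-life holds. That limits the concern without removing it, because marrow or liver effects need not follow plasma level.

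The result rests on counting study Days 1-10 from the first dose, which the documents imply but Section 3.2.1 does not state.

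It would be tempting to conclude that the AE rates will be understated. The documents do not show this. They do not say how many visits would be early, the window runs equally in both directions, and Section 11.4.3 tabulates events throughout the study with no cut at Day 10. No effect at cohort level is claimed. This is a cheap improvement of minor priority, not a threat to the study.

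**What to change.** 1. In Section 7.4 and Appendix A, change the Visit 08 window to Day 10 (+2 days).
2. In Section 3.2.1 and its restatement in Section 11, say that the period is study Days 1-10 counted from the first dose. This is clarification only. If the sponsor means a later starting point, the window must move with it.
3. In the Summary, Section 4 and Section 9.5.2, count a subject as complete for escalation only on or after Day 10.

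**Cost.** The permitted days go from five (Days 8-12) to three (Days 10-12), so each subject loses two scheduling days. The latest permitted day stays at Day 12.

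**Partial substitute.** If the present window is kept, an AE contact on or after Day 10 for each subject seen early would recover symptomatic events. It would not replace the safety panel, so the window change is preferable.
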